3.2.11 Body Surface Area

Due to the size of MLN8237 tablets, patients must be at least 0.38 m^2 to be eligible for the phase 2 portion of the study. There is no BSA limit for patients participating in the oral solution cohort.

3.2.12 Coexisting Medical Conditions

Patients with other ongoing serious medical issues must be approved by the study chair prior to registration.

3.3 Exclusion Criteria

- 3.3.1 Pregnancy, breast feeding, or unwillingness to use effective contraception during the study.
- 3.3.2 Patients status post-allogeneic stem cell transplant are not eligible.
- 3.3.3 Patients who, in the opinion of the investigator, may not be able to comply with the safety monitoring requirements of the study.
- 3.3.4 Patients with disease of any major organ system that would compromise their ability to withstand therapy.
- 3.3.5 Patients who are on hemodialysis.
- 3.3.6 Patients with an active or uncontrolled infection. Patients on prolonged antifungal therapy are still eligible if they are culture and biopsy negative in suspected radiographic lesions and meet other organ function criteria.
- 3.3.7 Known contraindication (eg allergy) to treatment with cefixime and cefpodoxime.
- 3.3.8 Patients with known intraparenchymal brain metastasis at study entry are excluded. Patients with metastasis to skull with intracranial extension are not excluded. Patients with a history of previous CNS metastasis only are required to have brain CT and/or MRI to exclude brain metastasis at study entry. Otherwise, in the absence of symptoms to suggest brain metastasis, dedicated CT or MRI of brain is not required prior to study entry.
- 3.3.9 Treatment with clinically significant enzyme inducers, such as the enzyme-inducing antiepileptic drugs phenytoin, carbamazepine or phenobarbital, or rifampin, rifabutin, rifapentine or St. John's wort within 14 days prior to the first dose of MLN8237 and during the study must not be used as these may interfere with irinotecan metabolism. Non-enzyme inducing anticonvulsants (Keppra, etc.) can be used after discussion with study chair.
- 3.3.10 Requirement for constant administration of proton pump inhibitor, H2 antagonist, or pancreatic enzymes. Intermittent uses of antacids or H2 antagonists are allowed as described in Section 4.7.6.
- 3.3.11 Known history of human immunodeficiency virus (HIV) infection, hepatitis B, or hepatitis C. Testing is not required in the absence of clinical findings or suspicion.

3.4 Regulatory

3.4.1 Informed Consent

The patient and/or the patient's legally authorized guardian must acknowledge in writing that consent to become a study subject has been obtained, in accordance with institutional policies approved by the US Department of Health and Human Services.

[figure not shown]
3.4.2 Protocol Approval

All institutional, FDA, and NCI requirements for human studies must be met.

4.0 TREATMENT PROGRAM

4.1 Treatment Overview

Cycle of Treatment

Prior to the start of each cycle of therapy, patients must meet organ function requirements listed in section 3.2.10, with the exception of platelet and ANC criteria which differ from entry criteria:

- Patients in any portion of the study entering the study with platelets \geq 100,000/uL (transfusion independent) and ANC \geq 1000/uL must recover to platelets \geq 75,000/uL (transfusion independent) and ANC \geq 750/uL (off any myeloid growth factors for more than 24 hours) prior to the start of the next cycle of therapy. Patients in the phase 2 portion entering the study with bone marrow disease and platelets $<$ 100,000/uL or ANC $<$ 1000/uL must recover to platelets \geq 50,000/uL (with transfusions) and ANC \geq 750/uL (off any myeloid growth factors for more than 24 hours) prior to the start of the next cycle.

Disease evaluation will take place during the third week of cycles 2, 4, 8, and then every 4 cycles. Patients may receive up to 34 cycles of therapy (~2 years) on study in the absence of dose-limiting toxicity (DLT) or progressive disease. Decisions regarding additional therapy on this study will be made by the study chair and treating physician in collaboration with the vice chair and sponsor.

4.2 Drug Administration

Please note the need for pharmacokinetic blood draws on Days 4 and 5 when choosing start date for Cycle 1.

Doses should be adjusted based upon height and weight obtained within 1 week prior to the start of each cycle.

Patients who enrolled during the Phase 1 portion and who remain on therapy should continue to follow guidelines for the oral solution cohort with the following exception: patients taking the enteric coated tablet no longer need to fast before or after MLN8237 except as indicated below.

4.2.1 MLN8237

MLN8237 will be given once daily by mouth on days 1-7 of each 21-day cycle. On days 1-5, the dose should be given one hour prior to the start of the irinotecan infusion and at the same time as the dose of temozolomide on those days.

For patients in the phase 2 portion, the dose of MLN8237 will be 60 mg/m^2 (dose level 2B) using exclusively the enteric coated tablet. The dose should be rounded to the nearest 10 mg using the dosing table in Appendix II, with doses capped at 2 m^2 . Tablets should not be crushed, split, or chewed. The dose can be taken either on an empty stomach or with food on Days 6 and 7, though on Days 1-5 should be taken without food as the dose is taken at the same time as temozolomide (see below). If a patient vomits after taking a dose, it should not be re-dosed.

For patients in the oral solution cohort, the dose of MLN8237 will be based upon the dose level assigned at study entry. The oral solution may be administered by mouth, via nasogastric tube, or via gastrostomy tube. The calculated dose should be rounded down to the nearest 0.5 mg (0.1 mL of the 5 mg/mL oral solution). The dose must be taken on an empty stomach (NPO two hours before and one hour after each dose). If a patient vomits after taking a dose, it should not be re-dosed.

EXAMPLES

- Assigned dose 45 mg/m^2 and BSA 0.83 m^2 → Calculated dose = 37.35 mg → Round down to 37.0 mg → Administer 7.4 mL of 5 mg/mL solution
- Assigned dose 45 mg/m^2 and BSA 0.84 m^2 → Calculated dose = 37.8 mg → Round down to 37.5 mg → Administer 7.5 mL of 5 mg/mL solution

For both formulations of the drug, systemic antacids (both H2 receptor antagonists and proton pump inhibitors) may alter MLN8237 exposure and should be avoided during MLN8237 treatment. Locally-acting antacids should not be taken simultaneously with MLN8237 but antacids can be given up to 2 hours prior or 2 hours following MLN8237 administration.

4.2.2 Temozolomide

Temozolomide will be given at a dose of $100 \text{ mg/m}^2/\text{dose}$ orally on days 1-5 of each 21-day cycle. The dose for patients $< 0.5 \text{ m}^2$ is $3.3 \text{ mg/kg}/\text{dose}$, respectively. The dose should be rounded based on the dosing table in Appendix III, with doses capped at 2 m^2 . The dose should be given one hour prior to irinotecan infusion and should be given at the same time as the dose of MLN8237. The dose should be taken on an empty stomach (NPO one hour before and one hour after each dose). If a patient vomits within 20 minutes of taking a dose, the dose should be re-dosed. If a patient vomits more than 20 minutes from taking a dose, the dose should not be re-dosed.

For patients unable to swallow pills, temozolomide capsules can be opened and drug administered using the instructions given in Appendix IV. Alternatively, an extemporaneous suspension can be prepared according to the instructions given in section 6.3.

4.2.3 Irinotecan

Irinotecan will be given at a dose of $50 \text{ mg/m}^2/\text{dose}$ IV over 1 hour on days 1-5 of each 21-day cycle.

For patients with double-lumen central venous catheters who will have pharmacokinetic sampling performed in cycle 1 (i.e. all patients in the oral solution portion of the study and consenting patients in the phase 2 portion of the study), the following administration routine will keep one lumen available for pharmacokinetic sampling and avoid the need for peripheral IV placement for pharmacokinetic sampling:

- Use the same lumen for each of the irinotecan infusions on days 1-4 (leaving one lumen unexposed to irinotecan);
- Run normal saline in the irinotecan unexposed lumen at a rate of 20 mL/hour starting 5 minutes before the start of the irinotecan infusion and continuing until 5 minutes after the completion of the irinotecan infusion;
- Flush and heparinize the irinotecan lumen following institutional standard practice while normal saline is still running in the irinotecan unexposed lumen;
- Flush with normal saline and heparinize the irinotecan unexposed lumen following institutional standard practice after the irinotecan lumen has already been flushed.

Since pharmacokinetic sampling is only performed in cycle 1, this routine need only be used in cycle 1.

4.2.4 Myeloid Growth Factor Support (required in all patients in Part B)
 All patients in Part B (dose levels ending in "B"; therefore all patients in the phase 2 portion and the oral solution cohort) receive myeloid growth factor starting on day 8 of the first cycle of therapy. The recommended regimen is filgrastim 5 micrograms/kg subcutaneously starting at least 24 hours after the last dose of MLN8237 and continuing until the ANC exceeds 2,000/ μ L post-nadir. Filgrastim must be discontinued at least 24 hours prior to the start of the next cycle of therapy. A single dose of pegfilgrastim (100 micrograms/kg; maximum dose 6 mg) given subcutaneously on day 8 may be substituted for filgrastim according to institutional standard practice.

4.2.5 Cephalosporin Diarrhea Prophylaxis (required in all patients in Part B)
 All patients in Part B (dose levels ending in "B"; therefore all patients in the phase 2 portion and the oral solution cohort) receive cephalosporin diarrhea prophylaxis with starting with the first cycle of therapy. The recommended regimen is cefixime 8 mg/kg/dose (maximum daily dose 400 mg) given orally once daily starting on day -1 (2 days before the start of irinotecan) and continuing until day +8 of each cycle. An alternative regimen is cefpodoxime 10 mg/kg/day (maximum daily dose 800 mg) divided twice daily starting on day -1 (2 days before the start of irinotecan) and continuing until day 8 of each cycle. If neither cefixime nor cefpodoxime are available, then another oral third generation cephalosporin may be substituted using standard dosing for that agent.

Patients who appear to be on schedule to begin a subsequent cycle of therapy on time should resume cephalosporin diarrhea prophylaxis on Day 20 of the current cycle (two days prior to planned Day 1 of the subsequent cycle).

4.3 Dose Escalation Schedule

In the completed phase 1 portion, the starting dose of MLN8237 was 45 mg/m²/day given orally once daily. This dose represented approximately 60% of the pediatric recommended phase 2 dose of 80 mg/m²/day from COG protocol ADVL0812. The dose escalation for the completed phase 1 portion is given below

Dose Escalation for the Completed Phase I Portion					
Dose Level	MLN8237 Oral (Days 1-7)	Irinotecan Intravenous (Days 1-5)	Temozolomide Oral** (Days 1-5)	Myeloid Growth Factor Support	Cephalosporin Diarrhea Prophylaxis
-1B	30 mg/m ² /day	50 mg/m ² /day	100 mg/m ² /day	Required	Required
1	45 mg/m ² /day	50 mg/m ² /day	100 mg/m ² /day	Optional	Optional
1B	45 mg/m ² /day	50 mg/m ² /day	100 mg/m ² /day	Required	Required
2B	60 mg/m ² /day	50 mg/m ² /day	100 mg/m ² /day	Required	Required
3B	80 mg/m ² /day	50 mg/m ² /day	100 mg/m ² /day	Required	Required

**See section 4.2.2 for doses in patients < 0.5 m².

With Amendment 5, the phase 2 portion of the study is open to patients who are able to swallow intact pills. All patients on the phase 2 portion will begin therapy at dose level 2B (60 mg/m²/day MLN8237) and will utilize the enteric coated tablet formulation.

With Amendment 5, a cohort evaluating an MLN8237 oral solution is open to patients who are not able to swallow intact pills. Based upon adult bioavailability data, evaluation of this oral solution cohort will begin at dose level 1B, with possible escalation to 2B or de-escalation to -1B based on pharmacokinetic data on dose level 1B. The dose will be assigned at study entry. These patients will be required to participate in pharmacokinetic testing.

Dose Escalation for Patients who are Unable to Swallow Intact Pills and Who will Receive the Oral Solution of MLN8237					
Dose Level	MLN8237 Oral (Days 1-7)	Irinotecan Intravenous (Days 1-5)	Temozolomide Oral** (Days 1-5)	Myeloid Growth Factor Support	Cephalosporin Diarrhea Prophylaxis
-1B	30 mg/m ² /day	50 mg/m ² /day	100 mg/m ² /day	Required	Required
1B	45 mg/m ² /day	50 mg/m ² /day	100 mg/m ² /day	Required	Required
2B	60 mg/m ² /day	50 mg/m ² /day	100 mg/m ² /day	Required	Required

**See section 4.2.2 for doses in patients < 0.5 m².

The dose level will be assigned at the time of patient registration. No intra-patient dose escalations are allowed.

4.4 Definition of Dose-Limiting Toxicity (DLT)

Toxicity will be graded using the CTCAE criteria, version 4.0. The CTCAE provides descriptive terminology and a grading scale for each adverse event listed. A copy of the CTCAE can be downloaded from the CTEP home page (<http://ctep.cancer.gov>). Any dose-limiting toxicity should be reported immediately through the NANT Operations Center to the Study Chair.

Definition of Inevaluable for Dose Escalation Evaluation

Patients who (1) receive < 5 of the 7 planned doses of MLN8237, < 4 of the 5 planned doses of irinotecan, or < 4 of the 5 planned doses of temozolomide in cycle 1 and (2) do not experience a DLT, will be replaced for the purposes of evaluating the dose level for dose escalation/de-escalation purposes (see Section 10.2.1).

Definition of Dose-Limiting Toxicity: Note that the definition of DLT changed with Amendment 6. Once a site has IRB approval of Amendment 6, the DLT definition and therefore dose modification decisions in Amendment 6 will be used for assessment and management of any new toxicities for patients enrolling prior to Amendment 6 and who remain on protocol therapy.

DLT is defined as any of the following events that are possibly, probably or definitely attributable to the combination of MLN8237, irinotecan, and temozolomide:

- Any grade 4 or 5 non-hematologic toxicity
- Any grade 3 non-hematologic toxicity, with the exception of:
 - Grade 3 nausea, vomiting, anorexia or dehydration resolving to < = grade 2 within 72 hours
 - Grade 3 transaminase elevation resolving to \leq grade 1 or baseline within 7 days of drug interruption/completion (if occurring on days 1-7 acceptable to continue drug through day 7 of course) or within 7 days of first occurrence if toxicity first occurs after drug completion. In either case, treating sites are to obtain repeat labs by the seventh day to determine whether the event meets DLT criteria.
 - Grade 3 diarrhea persisting for less than 72 hours
 - Grade 3 fever, infection or febrile neutropenia

- Grade 3 electrolyte disturbance resolving to < grade 1 or baseline within 7 days of drug interruption/completion (if occurring on days 1-7 acceptable to continue drug through day 7 of course) or within 7 days of first occurrence if toxicity first occurs after drug completion. In either case, supplementation is allowed and treating sites are to obtain repeat labs by the seventh day to determine whether the event meets DLT criteria.
- Start of next cycle of therapy later than day 36 due to non-hematologic toxicity and/or not meeting criteria to start subsequent cycle
- Dose-limiting neutropenia is defined as not meeting neutrophil criteria to start a subsequent course by day 36.
- Dose-limiting thrombocytopenia is defined as not meeting platelet criteria to start a subsequent course by day 36.

4.5 Treatment Duration

Patients may receive up to 34 cycles of therapy (~2 years) on study in the absence of progressive disease. Decisions regarding additional therapy on this study will be made by the study chair and treating physician in collaboration with the vice chair and sponsor. Patients experiencing dose-limiting toxicity (DLT) may continue to receive therapy modified as described in section 4.6.

4.6 Dose Modification

4.6.1 Thrombocytopenia

Patients evaluable for hematologic toxicity who develop dose-limiting thrombocytopenia (per section 4.4) should have their dose of temozolomide reduced to 75 mg/m^2 (see Appendix IIIB).

Patients who continue to have dose-limiting thrombocytopenia despite temozolomide dose reduction should have a bone marrow evaluation to exclude progressive bone marrow metastatic disease. In the absence of progressive bone marrow disease, these patients should have their dose of MLN8237 reduced by one dose level. Patients already receiving dose level -1B or an absolute dose of MLN8237 of 10 mg and who require dose reduction will be removed from protocol therapy.

Patients with recurrent dose-limiting thrombocytopenia despite dose reductions in both MLN8237 and temozolomide will undergo up to one additional dose reduction of MLN8237 and temozolomide. Temozolomide will be reduced first followed by MLN8237 in the next cycle if the combination continues to result in dose limiting thrombocytopenia. The dose of temozolomide should be reduced to $50 \text{ mg/m}^2/\text{dose}$, with dose rounded down to the nearest 5 mg. The dose of MLN8237 should be reduced by an additional dose level. Patients already receiving dose level -1B or an absolute dose of MLN8237 of 10 mg and who require dose reduction will be removed from protocol therapy.

Patients with recurrent dose-limiting thrombocytopenia despite two dose reductions in both MLN8237 and temozolomide will be removed from protocol therapy.

Patients who are not evaluable for hematologic toxicity due to low counts and bone marrow involvement at study entry who develop dose limiting thrombocytopenia should undergo bone marrow re-evaluation. If the bone marrow does not show progressive disease, then the dose modification strategy above should be followed.

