Amendment #5 also changes the dose modification procedures to utilize the existing dose levels rather than using 25% dose reductions. This change will facilitate dose rounding in a more uniform manner based upon the existing protocol dosing nomograms.

Amendment #5 also updates NANT response criteria, including criteria for evaluable disease.

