4.6.3 Mucositis

Patients who develop dose-limiting mucositis (per section 4.4) should have their dose of MLN8237 reduced by one dose level with their next cycle of therapy. Patients already receiving dose level -1B or an absolute dose of MLN8237 of 10 mg and who require dose reduction will be removed from protocol therapy.

Patients who continue to have dose-limiting mucositis despite initial MLN8237 dose reduction should have their dose of MLN8237 reduced by another dose level. Patients already receiving dose level -1B or an absolute dose of MLN8237 of 10 mg and who require dose reduction will be removed from protocol therapy.

If mucositis remains dose-limiting despite two MLN8237 dose reductions, temozolomide should be reduced to 75 mg/m² (see Appendix IIIB). Patients with recurrent dose-limiting mucositis despite these dose reductions should be removed from protocol therapy.

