4.6.4 Diarrhea

In addition to oral cephalosporin prophylaxis, other guidelines for patients with dose-limiting diarrhea include consideration of the possibility of cholinergic syndrome if diarrhea occurs within hours of the irinotecan infusion. Patients with early diarrhea may benefit from pretreatment with atropine (0.01 mg/kg IV; max dose 0.4 mg), as well as prolonging the irinotecan infusion to 90 minutes. Additional strategies for treating patients with therapy-associated diarrhea are given in section 5.5.

Patients who continue to have dose-limiting diarrhea despite cephalosporin prophylaxis and other measures above should have the dose of irinotecan reduced by 25% to 37.5 mg/m²/dose. These patients should continue to receive the above supportive therapies with subsequent cycles.

Patients with recurrent dose-limiting diarrhea despite supportive measures and irinotecan dose reduction should have the dose of irinotecan reduced by another 25% of the initial starting dose to 25 mg/m²/dose.

If diarrhea remains dose-limiting despite two irinotecan dose reductions, MLN8237 should be reduced by one dose level. Patients already receiving dose level -1B or an absolute dose of MLN8237 of 10 mg and who require dose reduction will be removed from protocol therapy. Patients with recurrent dose-limiting diarrhea despite these dose reductions should be removed from protocol therapy.

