4.6.5 Mood alterations

Patients who develop dose-limiting mood alteration while receiving MLN8237 should have the remainder of the MLN8237 for that cycle held. These patients should have their dose of MLN8237 reduced one dose level with their next cycle of therapy. Patients already receiving dose level -1B or an absolute dose of MLN8237 of 10 mg and who require dose reduction will be removed from protocol therapy.

Patients with recurrent dose-limiting mood alteration despite initial MLN8237 dose reduction should have their dose of MLN8237 reduced by another dose level. Patients already receiving dose level -1B or an absolute dose of MLN8237 of 10 mg and who require dose reduction will be removed from protocol therapy.

Patients with recurrent dose-limiting mood alteration despite these dose reductions will be removed from protocol therapy.

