4.6.6 Other toxicities

Patients who develop other dose-limiting non-hematologic toxicities (per section 4.4) should have their dose of MLN8237 reduced by one dose level. Patients already receiving dose level -1B or an absolute dose of MLN8237 of 10 mg and who require dose reduction will be removed from protocol therapy.

Patients with recurrent dose-limiting toxicity despite initial MLN8237 dose reduction should have their dose of MLN8237 reduced by another dose level. Patients already receiving dose level -1B or an absolute dose of MLN8237 of 10 mg and who require dose reduction will be removed from protocol therapy.

Patients with recurrent dose-limiting toxicity despite these dose reductions will be removed from protocol therapy.

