APPENDIX II. MLN8237 DOSING TABLES FOR PATIENTS RECEIVING ENTERIC COATED TABLETS

Patients receiving the oral solution should have their dose rounded according to section 4.2.1.

(Note that the surface area divisions change at each dose level for rounding purposes)

DOSE LEVEL -1B: 30 MG/M²/DOSE

Body Surface Area (m²)	Dose Level -1 (30 mg/m²)
0.38-0.49	10 mg
0.5-0.83	20 mg
0.84-1.16	30 mg
1.17-1.49	40 mg
1.5-1.83	50 mg
> 1.84	60 mg

DOSE LEVELS 1 AND 1B: 45 MG/M²/DOSE

Body Surface Area (m²)	Dose Level 1 (45 mg/m²)
0.38-0.55	20 mg
0.56-0.77	30 mg
0.78-0.99	40 mg
1.0-1.22	50 mg
1.23-1.44	60 mg
1.45-1.66	70 mg
1.67-1.88	80 mg
> 1.89	90 mg

DOSE LEVEL 2B: 60 MG/M²/DOSE

Body Surface Area (m²)	Dose Level 2 (60 mg/m²)
0.38-0.41	20 mg
0.42-0.58	30 mg
0.59-0.74	40 mg
0.75-0.91	50 mg
0.92-1.08	60 mg
1.09-1.24	70 mg
1.25-1.41	80 mg
1.42-1.58	90 mg
1.59-1.74	100 mg
1.75-1.91	110 mg
> 1.92	120 mg

DOSE LEVEL 3B: 80 MG/M²/DOSE

Body Surface Area (m²)	Dose Level 3 (80 mg/m²)
0.38-0.43	30 mg
0.44-0.56	40 mg
0.57-0.68	50 mg
0.69-0.81	60 mg
0.82-0.93	70 mg
0.94-1.06	80 mg
1.07-1.18	90 mg
1.19-1.31	100 mg
1.32-1.43	110 mg
1.44-1.56	120 mg
1.57-1.68	130 mg
1.69-1.81	140 mg
1.82-1.93	150 mg
> 1.94	160 mg

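### In three body-surface-area bands the required one-level MLN8237 reduction leaves the tablet dose unchanged, so Section 4.6 and Appendix II disagree on what a child receives after a DLT

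*Combined protocol and SAP*

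**What the plan says.** Sections 4.6.1 to 4.6.6 all reduce MLN8237 by dose level.

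- **Thrombocytopenia and neutropenia (4.6.1, 4.6.2):** after a first temozolomide reduction, "these patients should have their dose of MLN8237 reduced by one dose level". A further temozolomide cut and a further MLN8237 level can follow.
- **Mucositis (4.6.3):** patients with a DLT "should have their dose of MLN8237 reduced by one dose level with their next cycle of therapy". A second level follows on recurrence.
- **Diarrhea (4.6.4):** "If diarrhea remains dose-limiting despite two irinotecan dose reductions, MLN8237 should be reduced by one dose level". This is the only MLN8237 step on that route.
- **Mood alteration (4.6.5):** "These patients should have their dose of MLN8237 reduced one dose level with their next cycle of therapy", with a second level on recurrence.
- **Other non-hematologic DLTs (4.6.6):** patients "should have their dose of MLN8237 reduced by one dose level", with a second level on recurrence.

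Each section has one exit clause: a patient who needs a reduction but is already at level -1B, or already on an absolute dose of 10 mg, leaves protocol therapy.

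Section 2.12 explains that Amendment #5 "changes the dose modification procedures to utilize the existing dose levels rather than using 25% dose reductions", so that rounding follows the protocol's own dosing tables. For tablets those are in Appendix II, which warns "Note that the surface area divisions change at each dose level for rounding purposes". Section 4.2.1 starts phase 2 patients at 60 mg/m² (level 2B), tablets only, rounded to the nearest 10 mg, and forbids splitting. Section 3.2.11 sets the minimum BSA for phase 2 at 0.38 m². No passage says what happens when two adjacent levels give the same tablet dose.

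**The concern.** A dose-level reduction is ordered because the patient had a DLT, and its purpose is to lower exposure. If the table returns the same number of tablets, the instruction has been carried out on paper and the child is re-exposed to the same MLN8237 dose.

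This is most direct under 4.6.3, 4.6.5 and 4.6.6, where MLN8237 is the first drug reduced. Section 4.6.6 specifies no other change, so a child in a band where the first step is null restarts an identical regimen.

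The null step also uses up one of the allowed reductions. Later actions, including removal from therapy, depend on the reductions already made, so these children reach them with one fewer real reduction than the text implies.

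Finally, Section 10.6.1 tabulates toxicity by dose level. In these bands two different labels stand for the same administered dose.

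**Working it through.** **Inputs.** Level doses of 30, 45, 60 and 80 mg/m² for -1B, 1B, 2B and 3B (Section 4.3); the Appendix II tables; rounding to the nearest 10 mg with doses capped at 2 m² (Section 4.2.1); minimum BSA 0.38 m² (Section 3.2.11).

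**Step 1: reproduce the tables.** Tablet dose = level (mg/m²) × BSA, rounded to the nearest 10 mg, halves up. All four tables reproduce at every 0.01 m² from 0.38 to 2.00 (163 values), with no mismatch. The tables are therefore correct as rounding tables. The problem arises when they are used to implement a one-level step.

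**Step 2: where a null step can occur.** Levels 2B, 1B and -1B are 15 mg/m² apart. The calculated doses differ by less than one 10 mg tablet whenever 15 × BSA < 10, that is, BSA < 0.67 m². Below that size two adjacent levels can round to the same dose.

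**Step 3: compare adjacent levels at the same BSA.**

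| BSA (m²) | 2B | 1B | -1B | Null step |
|---|---|---|---|---|
| 0.38-0.41 | 20 mg | 20 mg | 10 mg | first (2B to 1B) |
| 0.42-0.49 | 30 mg | 20 mg | 10 mg | none |
| 0.50-0.55 | 30 mg | 20 mg | 20 mg | second (1B to -1B) |
| 0.56-0.58 | 30 mg | 30 mg | 20 mg | first (2B to 1B) |
| 0.59-0.74 | 40 mg | 30 mg | 20 mg | none |

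For example, at 0.57 m² level 2B is 60 × 0.57 = 34.2 mg, rounded to 30. Level 1B is 45 × 0.57 = 25.65 mg, also rounded to 30.

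**Step 4: count.** The bands hold 4 + 6 + 3 = 13 values. That is 13 of 21 between 0.38 and 0.58 m², and 13 of 163 (8%) over the whole grid. The first step is null at 4 + 3 = 7 values (7/163 = 4%) and the second at 6.

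**Step 5: compare with the other BSA values.** The nominal reductions are (60 - 45)/60 = 25% and (45 - 30)/45 = 33%. Where the tablet dose does change, the first step is a 14% to 40% cut (70 to 60 mg at 1.23-1.24 m²; 50 to 30 mg at 0.75-0.77 m²). The second is a 20% to 50% cut. Over both steps the nominal fall is 50%. At 0.50-0.58 m² the tablet dose falls from 30 to 20 mg, or 33%.

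**Step 6: check the exit clause.** Before each null step the child is at 2B or 1B on 20 or 30 mg, so neither condition is met. In Appendix II, 10 mg appears only at level -1B, so for tablets the 10 mg condition adds nothing to the -1B condition.

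**Step 7: completed phase 1 level.** Levels 3B and 2B both give 30 mg at 0.42-0.43 m². This could matter only for a phase 1 patient still on therapy at 3B.

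**The case against.** The strongest reply is that the two texts can both be followed. Levels are defined in mg/m², Section 4.6 orders a change of level, the nominal level does fall, and rounding to whole tablets is unavoidable. On that reading this is a rounding gap. That is fair as far as the label goes. But the text says the dose is to be reduced, and in these bands the table does not reduce it.

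Several limits on size stand:

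- The bands are narrow, and a count of table values is not a count of patients. Phase 2 enrolls 14-20 patients. An affected child must have a BSA of 0.58 m² or less and swallow whole tablets, so the number could be zero. The oral solution, rounded to 0.5 mg, is unaffected.
- Each band loses one step only. At constant BSA every child gets one real reduction over two steps.
- For hematologic DLTs temozolomide is cut first and MLN8237 moves at the second and fourth events. For diarrhea irinotecan is cut twice first, and a child starting at 2B cannot reach the 0.50-0.55 m² null through diarrhea alone.
- Before the null step these children are already 11-19% under nominal: 48.8-52.6 and 51.7-53.6 mg/m² against 60, and 36.4-40 against 45. After it, however, the same tablets are over the new nominal level: by 8-17% and 15-19% against 45, and by 21-33% against 30.

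Other safeguards help less. DLTs are reported to the Study Chair, and a physician may remove a patient for unacceptable toxicity, but neither says what dose to give. BSA is updated each cycle, yet growth does not remove the problem: level 1B stays at 20 mg up to 0.55 m² and at 30 mg up to 0.77 m², and -1B stays at 20 mg up to 0.83 m². Patient diaries (Section 13.0) document MLN8237 administration, so part of the exposure record may already exist. Rounding also separates nominal from actual dose across the whole table, so that reporting point is not peculiar to these bands.

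**Conclusion.** The concern holds. On the phase 2 path exactly three bands have a required one-level reduction that changes nothing: 0.38-0.41 and 0.56-0.58 m² at the first step, and 0.50-0.55 m² at the second. All lie within the eligible range, none is caught by the exit clause, and whole tablets leave a site no permitted way to give an intermediate dose.

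The result rests on the printed Appendix II tables and on BSA staying the same across the step. It does not depend on any outside figure. The number of patients affected cannot be derived, because the documents give no BSA distribution. It may be small, but the protocol expressly admits and doses these children, and the consequence for any one of them is re-exposure to the same MLN8237 dose after a DLT. This should be corrected.

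**What to change.** Reconcile Section 4.6 and Appendix II for BSA 0.38-0.41, 0.50-0.55 and 0.56-0.58 m², so that text and table agree on what happens when a required one-level reduction does not change the tablet dose. The same text should say whether such a step counts as a reduction when the later rules are applied. The clinical team must decide the rule; none is proposed here. If any phase 1 patient remains on level 3B, 0.42-0.43 m² needs the same attention.

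Separately, carry the administered MLN8237 dose in milligrams, alongside the nominal level, into the toxicity tables of Section 10.6.1.

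The cost is a note in Section 4.6 and Appendix II. It needs no new tablet strength, visits or patients.
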